- With the construct of the study, we would be keeping costs low by utilizing already established resources and practices (blood pressure cuffs, nurses, routine one week blood pressure checks) while only adding on the unit cost of furosemide and basic metabolic panels.
- If treatment with labetalol and furosemide is found to be useful, it would be not only a very inexpensive, cost effective way of improving patient outcomes and possibly decreasing lengths of stay, but possibly improvement in global practice in places that are lacking in resources privy to first world countries.

Methods

- A prospective randomized 1:1 controlled trial including postpartum women with gestational hypertension or preeclampsia
 - Inclusion criteria: Age 18-45, Postpartum: 24-72 hours after delivery, no contraindications to the study medications
 - Exclusion criteria: chronic hypertension diagnosis, creatinine levels above 1.5 $\mu\text{m}/\text{L}$, unable to give consent
- One arm receiving 200mg labetalol BID alone on Day#1 or at least 24 hours after magnesium sulfate, if given
- One arm receiving 200mg labetalol BID and a five day course of furosemide 20mg QD on Day#1 or 24 hours after magnesium sulfate
 - The 20 mg dose is the standard dose for furosemide in this population.
- Titrate labetalol to maintain blood pressures below 150 SBP and/or 100 DBP per ACOG recommendations.⁷
 - In the event of persistently elevated blood pressures, labetalol will be increased to 400mg BID and escalated to 600mg BID and finally 800mg BID as indicated
- Measurement of blood pressure every four hours until patient discharge
- Daily BMPs to assess for electrolyte abnormalities
- Measurement of urine output every 12 hours until discharge
- Demographics
 - Age (18-24, 25-34, 35-44, 45-51)
 - Nulliparous (yes, no)
 - BMI (underweight, normal, overweight, obese)

- Race (Caucasian, African American, Asian, Hispanic, Other)
- Diabetes (yes, no)
- Multiple gestation (yes, no)
- Preterm delivery (yes, no)
 - Gestational age at delivery
- Cesarean delivery (yes, no)
- IVF pregnancy (yes, no)
- History of previous gestational hypertension/pre-eclampsia (yes, no)
- Systemic lupus erythematosus (yes, no)
- Renal disease (yes, no)
- Outcome variables
 - Need for additional antihypertensive medication (yes, no)
 - Labetalol 400mg BID
 - Labetalol 600mg BID
 - Labetalol 800mg BID
 - Highest systolic blood pressure (mmHg)
 - Highest diastolic blood pressure (mmHg)
 - Mean arterial blood pressure

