 - Daily urine output (mL)
 - Length of postpartum stay (days)
 - Readmission for hypertension (yes, no)
 - Breastfeeding at 1 week postpartum (yes, no)
- The study duration is the length of the hospital stay plus 1 week postpartum blood pressure check.
- The research will be analyzed and interpreted by the research team conducting the study.
- Potential difficulties and limitations include compliance concerns of mandatory one week blood pressure follow up appointment.
- The unit cost of one tablet of labetalol 200mg and furosemide 40mg is currently \$0.32 and \$1.23, respectively.^{8,9}
- The study would use already readily available automated blood pressure cuff machines on the postpartum wing.

Safety Monitoring

Monitoring of blood pressures will be performed every four hours while on the maternity postpartum floor. If the patient is found to be above 160 systolic or 110 diastolic, it will be rechecked in fifteen minutes. If still elevated, then escalation of blood pressure medicine will be done. The healthcare provider will ask the patient if they are exhibiting any signs of profound hypertension and/or hypokalemia including headache, vision changes, dizziness, lightheadedness, weakness, fatigue, muscle cramping, or heart palpitations. If any of these are identified, a physician will be notified and will assess the patient.

Patients will be instructed to let their doctor/nurses know if they are experiencing known side effects of Lasix that include new onset weakness, fatigue, muscle cramping, dizziness or

heart palpitations. If a patient has severe symptoms after discharge, they will be instructed to call the afterhours phone number on the consent form.

If a patient has signs of hypokalemia, we will test lab values for potassium (K+) levels (Complete metabolic panel). We will continue administering Lasix if the potassium result is between 3.0 and 3.4 $\mu\text{m}/\text{L}$ and we will administer 20 mEq KDur BID. If it is less than 3.0 $\mu\text{m}/\text{L}$ we will stop using Lasix.

References

- 1) Veena, P., et al. “Furosemide in Postpartum Management of Severe Preeclampsia: A Randomized Controlled Trial.” *Hypertension in Pregnancy*, vol. 36, no. 1, 2016, pp. 84–89., doi:10.1080/10641955.2016.1239735.

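### The only potassium limits for continuing or stopping furosemide are written for a symptom-triggered test; the daily metabolic panels already being drawn have no action attached

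*Protocol*

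**What the plan says.** Two parts of the protocol deal with potassium.

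- **Safety Monitoring** starts from symptoms: "If a patient has signs of hypokalemia, we will test lab values for potassium (K+) levels". The same sentence names the test as a complete metabolic panel. The limits come next. The first is "We will continue administering Lasix if the potassium result is between 3.0 and 3.4", paired with "we will administer 20 mEq KDur BID". For a result under 3.0 the instruction is "we will stop using Lasix".
- **Methods** lists, among the inpatient measurements, "Daily BMPs to assess for electrolyte abnormalities". That line gives a purpose but no limit and no action.

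The Significance section counts basic metabolic panels among the study's added costs, so these tests are already planned. The SAP covers the primary and secondary efficacy comparisons and contains no laboratory or safety rule. (The unit printed beside the potassium limits is a separate matter, left aside here.)

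**The concern.** The limits for replacing potassium or stopping the trial drug depend on a woman showing signs of hypokalemia. The trial will nevertheless have a potassium value for her each day from the panel, drawn to find electrolyte problems, and nothing says what to do with it. This is the only written furosemide stop rule in either document. A woman with a low value and no symptoms could therefore stay on furosemide without departing from the protocol, and two such women could be managed differently by different staff. She could also be sent home part-way through the course without her last value having been compared with the limits. A trigger based on the laboratory result would be safer than one based on symptoms, and the data for it are already being collected.

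**Working it through.** The plan states no figure for this point, so the check is a reading of the text. Its one computed design figure, 96 patients per group, does not enter the argument. For completeness it does reproduce: with 26% versus 8%, two-sided alpha 0.05 and the Fisher's exact test named in the SAP, full binomial enumeration gives power of 89.9% at 95 per group and 90.3% at 96.

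**Step 1: which result do the limits refer to?** The paragraph runs in order: signs of hypokalemia, then a test, then what to do with the potassium result. The nearest referent for that result is the test just named. The test is described as "potassium (K+) levels (Complete metabolic panel", whereas Methods orders basic metabolic panels. The different name supports reading it as a separate test.

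**Step 2: is an action attached to the daily panels elsewhere?** The Methods line has none. The rest of Safety Monitoring covers blood pressure rechecks, questions about symptoms, and instructions to patients. The SAP has nothing on laboratory values. So no.

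**Step 3: the cases for a woman in the furosemide arm, read literally.**

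- Signs of hypokalemia, potassium below 3.0: furosemide stops.
- Signs of hypokalemia, potassium 3.0 to 3.4: furosemide continues and potassium is replaced.
- No signs, daily panel below 3.0: no written stop rule.
- No signs, daily panel 3.0 to 3.4: no written replacement.

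The last two cases are the gap.

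**Step 4: would closing it disturb the primary analysis?** The SAP compares the groups as randomized on whether the labetalol dose was escalated during the hospital stay. A potassium supplement is not a labetalol escalation, so it does not touch the endpoint. A woman who stops furosemide early remains in her randomized group. A few extra stops could dilute the contrast slightly, and only among women with potassium below 3.0. The sample size calculation, alpha and test do not change.

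**The case against.** The strongest reply is that the two parts should be read together. Methods says why the panels are drawn and Safety Monitoring says what potassium values call for, so a sensible clinician would apply the limits to any result and treat symptoms as a reason for an extra test. That reading is open, and staff on a single postpartum wing would probably act on a low value. The symptom trigger is also broad: providers ask about weakness, fatigue, dizziness, cramping and palpitations, and a physician assesses anyone who reports them, so many women with low potassium would reach the test anyway. These arguments limit the weight of the point. They do not remove it, because neither the joint reading nor a laboratory trigger is written, and a stop rule for the trial drug should not depend on inference.

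A reader might infer more than the documents support:

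- **That potassium goes unmonitored.** It does not; it is measured daily.
- **That the panels are open-ended because their line gives no stopping point.** The line sits between "Measurement of blood pressure every four hours until patient discharge" and "Measurement of urine output every 12 hours until discharge", so daily most naturally means while in hospital. Adding an end date would be editorial.
- **That women are unprotected after discharge.** Patients are already told to report furosemide side effects and to call if symptoms are severe. The consent form is not in the reviewed copy, and length of stay is not stated, so the number of doses taken at home is unknown.
- **That a number of women harmed can be estimated.** The documents give no rate of hypokalemia, with or without symptoms. Any probability would rest on an invented rate, and a count of scheduled panels would consist partly of normal results that need no action.

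**Conclusion.** The point holds as a minor safety correction. The written limits follow a symptom-triggered test, the daily panels carry no action, and nothing else in the protocol or SAP closes the gap for a symptom-free woman on furosemide with potassium below 3.0 or at 3.0 to 3.4.

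This rests on a literal reading of the Safety Monitoring paragraph. If the investigators always meant the limits to cover every result, the change only confirms their intent. If they did not, it corrects a rule that waits for symptoms when a value is already in hand. The effect on the primary analysis is negligible, and no numerical size can be given for the safety effect.

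**What to change.** Keep the symptom-triggered test and add one sentence to Safety Monitoring:

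> *In the furosemide arm, the 3.0 and 3.4 limits and actions apply to every potassium result, including each daily BMP and the last result before discharge on furosemide, whether or not the woman has symptoms.*

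The restriction to the furosemide arm is needed because the Methods line does not limit the panels by arm, and an instruction to continue or stop furosemide means nothing for women on labetalol alone.

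The actions stay as the protocol has them. Below 3.0 the only written action is to stop furosemide; this sentence does not add replacement there.

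The cost is one sentence and no new scheduled test. The downside is a few more KDur starts or early furosemide stops.

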Postpartum management of gestational hypertensive disorders using furosemide: A randomized controlled trial

Statistical Analysis Plan

Version Jan 9, 2020

[name]; [name], DO; [name]

The statistical analysis plan is based on the objectives of the study as follows:

Main Question: Does the use of furosemide plus labetalol improve blood pressures in the postpartum period of patients with gestational hypertensive disorders versus labetalol alone?

Primary:

Does the addition of a 5-day course of furosemide to labetalol avoid the escalation of anti-hypertensive therapy to control blood pressures.

Analysis plan: Randomization groups (labetalol + furosemide vs labetalol alone) will be compared using a Fisher's Exact test for number of patients who have had an escalation of labetalol dose at any time during their hospital stay.

Secondary:

Does the addition of furosemide to labetalol in postpartum hypertension:

1. Improve of systolic blood pressure, diastolic blood pressure and mean arterial pressure.

Analysis plan: Randomization groups will be compared on daily means for each outcome by repeated measures ANOVA to determine difference in outcomes across time (Day 0/Baseline, Day 1, and Day 2). One repeated measures ANOVA will be performed for each of the three outcomes (systolic blood pressure, diastolic blood pressure, and mean arterial pressure).

2. Shortened hospital stay

Analysis plan: Randomization groups will be compared on hospital length of stay using a Student T-test.

3. Affect breastfeeding status at 1 week postpartum visit in mothers planning to breastfeed.

Analysis plan: Randomization groups will be compared on breastfeeding status at the postpartum visit using a Fisher's Exact test.

4. Decrease readmission for postpartum hypertensive disorders.

Analysis plan: Randomization groups will be compared on the number of participants who were hospitalized after discharge using a Fisher's Exact test.

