Research Proposal
[name], DO
WSU-SOM, OBGYN, PGY-2

Title

- Postpartum management of gestational hypertensive disorders using furosemide: A randomized controlled trial

Investigators

- Primary Investigator
 - [name], DO, PGY-2, Capt, USAF
 - [contact]
 - [contact]
- Investigators
 - [name], MFM subspecialist at MFMUG
 - [contact]
 - [contact]
 - [name], WSU-SOM Teaching Faculty
 - [contact]
 - [contact]

Summary

- The main purpose of this study is to learn if incorporating a loop diuretic such as furosemide along with labetalol in the routine management of postpartum gestational hypertensive disorders could lower the need for additional anti-hypertensive agents to control blood pressures, improve blood pressures (as measured by systolic blood pressure, diastolic blood pressure and mean arterial blood pressures), shorten hospital stays and decrease readmissions for patients with gestational hypertensive disorders.
- Based on a study by Veena et al¹, there is reason to believe that the addition of furosemide to other anti-hypertensives may help decrease the need to add or increase the dose of medication to control blood pressures. There may be potential to shorten hospital stays and decrease readmissions, as well. Collecting data will be done using a prospective, randomized 1:1 controlled study assigning postpartum patients with a gestational hypertensive diagnosis to either labetalol alone or labetalol plus furosemide.
- Based on an estimated 8% need for increase in anti-hypertensive medication in the furosemide group and a 26% need in the standard treatment arm, to achieve 90% power

with a 2-sided alpha of 0.05, we calculate 96 patients per group. Analysis will be via Chi-square or Fisher's exact test for categorical variables. Student T-Test and Mann Whitney U tests will be utilized to compare continuous variables. Randomization will be performed using REDCap.

- The study will be performed in the postpartum wing of Miami Valley Hospital Main Campus and would recruit patients who have consented to participate in the study with enrollees coming from the OB Staff population.

Background and Literature Review

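### The primary test counts only in-hospital labetalol dose increases, while the objective covers any escalation of antihypertensive treatment, so a second agent given without a labetalol increase is scored as a success

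*SAP*

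**What the plan says.** The event is described broadly in five places.

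- **SAP, Primary objective** (same wording in protocol Objectives): the question is whether furosemide helps "avoid the escalation of anti-hypertensive therapy to control blood pressures". No drug is named.
- **Protocol, Summary, purpose:** the combination "could lower the need for additional anti-hypertensive agents to control blood pressures".
- **Protocol, Summary, rationale:** furosemide may "decrease the need to add or increase the dose of medication to control blood pressures". This covers a new drug as well as a higher dose.
- **Protocol, Summary, sample size:** the 8% and 26% rates are described as a need to increase antihypertensive medication, again with no drug named.
- **Protocol, Methods, Outcome variables:** the label is "Need for additional antihypertensive medication (yes, no".

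It is described narrowly in three.

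- **SAP, Primary, Analysis plan:** the test compares the "number of patients who have had an escalation of labetalol dose at any time during their hospital stay".
- **Protocol, Methods, Outcome variables:** the only items under the label above are labetalol at 400, 600 and 800 mg BID.
- **Protocol, Methods, titration:** for persistently raised pressure, "labetalol will be increased to 400mg BID and escalated to 600mg BID and finally 800mg BID as indicated". No second agent is named.

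Protocol Safety Monitoring falls between the two. After a confirmed severe reading it says "If still elevated, then escalation of blood pressure medicine will be done", without naming an agent.

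**The concern.** The objective and the test do not describe the same event. A woman given a second antihypertensive, with no labetalol increase at any time in hospital, has had her therapy escalated in the sense of the objective. The SAP nevertheless scores her as a non-event. Neither document prohibits a second agent or says how one is to be scored, and the listed outcome fields have no place to record one.

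Two things are at stake. If such cases occur equally in both arms, events are lost and power falls. If they occur unequally, the comparison is biased. The second is possible because no blinding or placebo is described: the choice between raising labetalol and adding another drug may be made by someone who knows the arm.

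**Working it through.** **1. Reproduce the plan's figure.** Inputs from the protocol Summary: 8% vs 26%, two-sided alpha 0.05, 90% power, 1:1 allocation, 96 per group. The test is the SAP's Fisher's exact test.

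Power = sum over all (x, y) with two-sided Fisher p ≤ 0.05 of Bin(x; n, p_F) × Bin(y; n, p_C), where F is furosemide and C is control.

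- n = 95: 0.8995
- n = 96: 0.9032

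The stated 96 is the first n to reach 90%, so the sample size arithmetic is sound.

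**2. Who is misclassified.** The SAP counts a labetalol increase at any time during the stay.

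| In-hospital course | Escalated under the objective? | Event in the SAP test? |
|---|---|---|
| Labetalol raised, no other agent | yes | yes |
| Labetalol raised, other agent before or after | yes | yes |
| Other agent, labetalol never raised | yes | **no** |
| Neither | no | no |

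Only the third row is affected.

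**3. Size, by assumption.** Let m be the share of true escalations that fall in the third row. The documents give no value; 10% to 30% is an illustrative range. Observed rate = true rate × (1 − m).

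*Equal shares in both arms, true rates 26% vs 8%, n = 96 per arm:*

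| m | Control | Furosemide | Fisher power |
|---|---|---|---|
| 0 | 26% | 8% | 0.903 |
| 10% | 26 × 0.9 = 23.4% | 8 × 0.9 = 7.2% | 0.859 |
| 20% | 26 × 0.8 = 20.8% | 8 × 0.8 = 6.4% | 0.800 |
| 30% | 26 × 0.7 = 18.2% | 8 × 0.7 = 5.6% | 0.724 |

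*Missed in the control arm only, furosemide staying at 8%:* power is 0.808, 0.665 and 0.483 at m = 10%, 20% and 30%.

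*Missed in the furosemide arm only, with no true difference (26% in both arms):* the two-sided rejection rate is 0.035 with none missed, and 0.051, 0.105 and 0.209 at m = 10%, 20% and 30%.

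*Direction of bias, with an assumed true 26% vs 16% (difference 10 points):*

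- 10% missed in control, 30% in furosemide: 26 × 0.9 = 23.4% vs 16 × 0.7 = 11.2%, difference 12.2 points.
- 30% missed in control, 10% in furosemide: 26 × 0.7 = 18.2% vs 16 × 0.9 = 14.4%, difference 3.8 points.

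The same true effect therefore looks larger or smaller according to which arm loses more events.

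**The case against.** The strongest reply is that the SAP follows the protocol's own operational definition. The three items under the outcome variable are labetalol doses, and labetalol titration is the only escalation pathway written down. The unspecified escalation in Safety Monitoring can be read as that same ladder. A woman treated along the ladder who later receives a second drug is already an event. This stands, and it confines the gap to women given another agent with no labetalol increase at all. It does not remove the conflict with the objective, the purpose, the outcome label and the sizing wording, and a planned ladder does not settle how a departure from it is scored.

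A reader might infer more than the documents support:

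- *That the SAP departs from the protocol.* It matches the protocol's listed items; the broad and narrow wordings already coexist inside the protocol.
- *That treatment failures will be counted as successes on a material scale.* Neither document mentions use of a second agent, an acute agent, or furosemide in controls. The shares above are assumptions, and on a labetalol-first ladder the lost share could be small.
- *That the 26% and 8% belong to a different endpoint.* Their wording can include a dose increase, and the event definition behind them is not given. The mismatch is possible but not shown.
- *That control-arm furosemide should itself be a primary event.* That component would fall mainly on controls, since the other arm already receives the drug. It also needs a judgement about the reason for use in a trial with no described blinding, so it could favour furosemide.

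**Conclusion.** The concern holds in a limited form. The primary test is narrower than the objective it serves, and a woman given another antihypertensive with no in-hospital labetalol increase is scored as having avoided escalation. The size is unknown. If 10% to 30% of escalations were missed equally in both arms, power would be 0.86 to 0.72 instead of 0.90; unequal shares could bias the result either way. These figures assume that 26% and 8% are the true rates for the broader event (except in the examples labelled otherwise) and that none of the missed women ever had labetalol raised. The planned 96 per group is not in question. This should be fixed because it concerns the definition of the primary event and costs little. It is not a fatal fault, because the SAP agrees with the protocol's listed items and only written ladder, and the harm depends on treatment outside that ladder.

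**What to change.** Reconcile the passages so that one definition serves throughout.

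1. In SAP Primary, and under the protocol's outcome variable, define the event as: any increase in labetalol dose above the assigned starting dose, or any additional (non-study) antihypertensive agent started during the hospital stay.
2. Add one yes/no field for another agent, taken from the medication record.
3. Report the labetalol-only count as a supporting analysis.
4. Handle off-protocol furosemide in the control arm in a prespecified sensitivity analysis, not in the primary event.

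If labetalol-only is truly intended, narrow the objective to labetalol dose escalation instead and justify 26% vs 8% for that endpoint.

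The cost is a wording change in both documents, one data field, the supporting count and the sensitivity analysis. The sample size stays at 96 per group provided that 26% and 8% describe the broader event, as the Summary's wording suggests. The change concerns scoring only and alters no dose or treatment rule.

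### The unadjusted Fisher's exact test meets the planned 90% power, but a pre-specified analysis adjusted for pre-dose blood pressure would get more from the same 192 patients

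*SAP*

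**What the plan says.** The primary analysis plan in the SAP is a single Fisher's exact test on the "number of patients who have had an escalation of labetalol dose at any time during their hospital stay". It names no covariate and no supporting adjusted model. The Protocol Summary offers only chi-square or Fisher's exact tests for categorical variables.

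The sample size is in the Protocol Summary. It rests on an "estimated 8% need for increase in anti-hypertensive medication in the furosemide group" and "a 26% need in the standard treatment arm", and is set "to achieve 90% power" "with a 2-sided alpha of 0.05, we calculate 96 patients per group". The design is a "prospective, randomized 1:1 controlled study", randomised through REDCap.

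Blood pressure is collected throughout. The Protocol Methods require "Measurement of blood pressure every four hours until patient discharge". SAP Secondary 1 uses daily means "to determine difference in outcomes across time (Day 0/Baseline, Day 1, and Day 2"), so the SAP already recognises a baseline pressure, but only for the secondary repeated measures ANOVAs. Baseline pressure is not in the list of demographics in the Protocol Methods.

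**The concern.** The primary outcome is a reaction to blood pressure. All patients start labetalol at the same dose, and it is raised when pressure stays high. A woman whose pressure is already near the trigger has less room before she counts as an event. A pre-treatment pressure is thus a natural prognostic covariate, and the primary test does not use it. Fisher's test is also conservative: at these group sizes it rejects a true null less often than the nominal 5%.

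What is at stake is power on the primary endpoint, mostly if the true effect is smaller than planned. The planning effect is a drop from 26% to 8%. The Protocol background describes the supporting trial as furosemide with nifedipine in severe pre-eclampsia, whereas this trial adds furosemide to labetalol in gestational hypertension or preeclampsia. The planned drop may not carry over.

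**Working it through.** **Inputs from the Protocol Summary.** Escalation rates 0.26 (labetalol alone) and 0.08 (with furosemide); two-sided alpha 0.05; power 90%; 1:1 allocation; 96 per group.

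**Input assumed.** The strength of baseline pressure as a predictor of escalation, as an odds ratio (OR) per SD. Neither document gives it. The range considered is 1 (no prediction) to 3, which corresponds to an AUC of 0.50 to about 0.76.

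**Step 1: reproduce the plan's figure.** Power is the sum of Bin(a; n, 0.26) × Bin(b; n, 0.08) over all pairs (a, b) for which the two-sided Fisher p-value is at most 0.05.
- n = 95: 89.9%
- n = 96: 90.3%

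So 96 is the first n to reach 90% with Fisher's test. For comparison, the pooled normal formula gives 90 per arm and the continuity-corrected one 101.

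**Step 2: cost of Fisher's conservatism.** The same enumeration under equal rates gives a true size of 3.3% at a common rate of 17% (the mean of 26% and 8%) and 3.5% at 26%. An unadjusted chi-square test at 96 per arm, 26% versus 8%, has power 93.1%. The gain is 93.1 − 90.3 = 2.8 points with no covariate.

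**Step 3: what the covariate adds.** Trials of 96 per arm were simulated with logit P(escalation) = a(arm) + log(OR) × x, x standard normal, and intercepts solved to hold the marginal rates fixed. Arm was tested by likelihood ratio in a logistic model containing x. There were 4,000 trials per cell. Ranges for Fisher and chi-square are simulation noise.

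| True rates | Fisher | Chi-square | Adjusted, OR 1 | OR 1.5 | OR 2 | OR 3 |
|---|---|---|---|---|---|---|
| 26% vs 8% | 90-91% | 92-93% | 92.9% | 93.9% | 93.6% | 96.3% |
| 26% vs 10% | 78-80% | 83-84% | 84.7% | 85.4% | 85.9% | 88.9% |
| 26% vs 13% | 56-57% | 63-64% | 63.6% | 64.8% | 67.0% | 69.9% |
| 26% vs 26% (type I error) | 3.4-3.8% | 4.8-5.4% | 5.0% | 5.2% | 5.5% | 5.6% |

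The Monte Carlo standard error near 93% is √(0.93 × 0.07 / 4000) = 0.4 points; near 64% it is √(0.64 × 0.36 / 4000) = 0.8 points. A separate run of 5,000 trials per cell at 26% versus 8% gave 92.9%, 93.3%, 94.5% and 96.1% for OR 1, 1.5, 2 and 3. A third run put the upper end at 26% versus 13% at 71%. A test of the standardised risk difference from the same model had the same power to within 0.2 points.

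**Step 4: split the gain at the planning rates.** Leaving Fisher: about 3 points. The covariate: 93% to about 96%, so 0 to 3 points. At 26% versus 13%, leaving Fisher gives about 63 − 57 = 6 points and the covariate 0 to 8 more.

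**Step 5: how many covariates the data can carry.** Expected events are 0.26 × 96 + 0.08 × 96 = 24.96 + 7.68 = 32.64, about 33, with only about 8 in the furosemide arm. One covariate is reasonable; a longer list is not.

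**The case against.** The strongest reply is that nothing is broken. The sample size matches Fisher's test, so its conservatism has already been paid for in patients. A reader might infer that the trial is underpowered because it uses this test. The documents do not support that: the planned power is met at the planned rates. This part of the reply stands in full.

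A reader might also infer that omitting baseline pressure is the main loss, or that baseline pressure drives escalation. Neither is shown. At the planning rates about half or more of the gain comes from leaving Fisher, and the Protocol already allows a chi-square test. Escalation is tied to pressure during treatment, and no association with baseline is reported. The trigger itself is not settled. The Protocol Methods titrate to 150/100, while Safety Monitoring escalates above 160/110 after a recheck. Those passages must be reconciled before anyone can say how predictive baseline will be.

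The SAP's Day 0 value is a daily mean, and nothing says its readings precede the first study dose. Adjusting for a partly post-dose value could bias the primary comparison. This stands and shapes the fix.

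With few events, preferring a test that keeps its size below 5% is defensible. That is a real trade-off, though a small one: simulated type I error for the adjusted test is about 5-6%.

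Finally, chance imbalance in baseline pressure is only a minor argument. The unadjusted test remains valid under randomisation. Silence about stratification does not establish that there is none.

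What the reply does not remove is that adjusted power was above Fisher's in every alternative simulated, even with a useless covariate, and that the gain is larger if the effect is smaller than planned.

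**Conclusion.** The point holds as an inexpensive improvement to the primary analysis, not as an error. Fisher's test gives 90.3% power at 96 per arm for 26% versus 8%, as planned. A chi-square test would give 93.1%, and an analysis adjusted for baseline pressure about 93% if baseline predicts nothing, rising to about 96% at an odds ratio of 3 per SD. If the true rates were 26% versus 13%, the figures would be about 57%, 63% and 64-71%.

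The Fisher and chi-square figures follow from the Protocol's own inputs, apart from the alternative rate of 13%, which is an assumption. The covariate's contribution rests wholly on the assumed odds ratio. All figures assume 96 evaluable patients per arm, since the documents give no dropout allowance.

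**What to change.** Before any outcome is seen by arm, amend the primary analysis in the SAP as follows.

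- **Model.** Logistic regression of escalation (yes/no) on randomised arm and baseline mean arterial pressure, with arm tested by likelihood ratio.
- **Baseline.** Define it as the last reading or readings before the first study dose, not as the Day 0 daily mean. Add it to the baseline variables listed in the Protocol Methods, and state what is done if it is missing.
- **Estimate.** Report the standardised risk difference with its 95% CI. This keeps the marginal comparison on which the sample size is based; the model's own odds ratio is conditional on baseline.
- **Supportive analysis.** Keep Fisher's exact test, labelled as unadjusted.
- **Covariates.** Use this one only, given about 33 expected events.

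The cost is some SAP wording, one more baseline field taken from readings the ward should already have, and a few lines of code. No extra patients or visits are needed. The downside is that the main p-value is no longer exact and its simulated type I error is about 5-6%, against under 4% for Fisher. If the team prefers to keep an exact primary test for that reason, the plan still meets its stated power, and the adjusted model can be pre-specified as supportive.
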